9.2 General

A statistical analysis plan (SAP) will be prepared prior to data lock to expand and provide further details on the analysis and presentation of data described below.

Demographic data and disease-related characteristics will be summarized using descriptive statistics (count and percent, mean, median, standard deviation, minimum, maximum). All patient data, efficacy and safety, will be summarized similarly and fully listed.

9.3 Analysis Populations

The following populations will apply:

Safety Evaluable Population: All patients who received study medication (APR-246 or PLD) will be considered evaluable for safety regardless of the duration of treatment. This population will be used

to summarize all safety parameters.

Efficacy Evaluable Population: All patients with pretreatment measurable disease by RECIST 1.1 who have at least one radiographic assessment after pretreatment or discontinue study medication early due to disease progression and have a p53 mutation will be considered evaluable for efficacy. The efficacy-evaluable population will be the primary analysis population for efficacy.

9.4 Statistical Methods

All demographic data and disease-related characteristics will be summarized using descriptive statistics (count and percent, mean, median, standard deviation, minimum, maximum).

9.4.1 Efficacy Data

Overall Response Rate

Best overall response according to RECIST 1.1 will be presented along with the associated exact Clopper-Pearson 2-sided 95% and 1-sided lower 90% binomial confidence limits [20].

Progression-free Survival

PFS is defined as the time from registration to the time of disease progression or relapse (according to RECIST 1.1 only) or death. Patients who do not experience a PFS event will be censored at their last clinic visit contact for the assessment of disease progression.

PFS time will be summarized via a Kaplan-Meier curve with 95% confidence interval. Median PFS will be estimated from the Kaplan-Meier and presented long with 2-sided 95% confidence limits using the method of Brookmeyer and Crowley (1982) [21]. The PFS rate at 3, 6 and 9 months' follow-up will also be presented together with 2-sided 95% confidence limits using the method of Klein (2007) [22].

Evaluation of Biomarkers

The relationship between biomarkers and efficacy in terms of PFS and RECIST response will be explored using logistic regression methodology and accelerated failure time analysis.

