9.1 Sample Size

The aim is to determine the preliminary efficacy of APR-246 with PLD. The endpoint of interest is the ORR as defined in Section 8.3.2.2.

A two stage design is used to test the null hypothesis that the true response rate of APR-246 in combination with PLD is $\leq 10\%$ versus the alternative that the true response rate is $\geq 30\%$. In the first stage, 16 patients will be assessed for response; if ≤ 1 response is seen in these 16 patients the study will be curtailed for futility. Otherwise the study will continue and a further 9 patients will be entered, for a total of 25 evaluable patients. If ≥ 5 responses are observed in these 25 patients, the null hypothesis will be rejected in favor of the alternative. This design provides 90.3% power and a 1-sided alpha of 9.5%.

Sub-Study Sample Size:

The aim is to determine the safety, tolerability and efficacy of a shorter infusion of APR-246 with PLD. The endpoint of interest is safety.

At one of the shorter infusion levels (3 hr 4.5 g, 4 hr 4.5 g, or 4 hr 3.7 g) if there are 0 or 1 out of 6 patients with DLTs across the first 6 patients, then an additional 8 patients will be treated for an initial total of N=14. If 0 or 1 out of 14 responses are seen, then recruitment will cease. If 2 or more out of 14 responses are seen, a further 11 patients will be recruited for a total of N=25. Observance of 5/25 responses will result in rejection of the null hypothesis. The design carries 89% power and a 1-sided type I error of 9.1% to test the null hypothesis that the true response rate is $\leq 10\%$ vs the alternative that the true response rate is 30%.

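### Section 9.4.1 puts fixed-sample Clopper-Pearson limits on a two-stage response rate, so the 95% interval is not exact and its upper limits are too low at 2 to 4 responses in 25

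*Combined protocol and SAP*

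**What the plan says.** Section 9.1 states that "A two stage design is used to test the null hypothesis" of a 10% response rate against 30%. For the Main Study, "In the first stage, 16 patients will be assessed for response"; with 0 or 1 "response is seen in these 16 patients the study will be curtailed for futility". Otherwise "a further 9 patients will be entered, for a total of 25 evaluable patients", and 5 or more responses reject the null. The Sub-Study has the same structure with a first stage of 14: "If 0 or 1 out of 14 responses are seen, then recruitment will cease"; otherwise it goes on to 25, and 5/25 rejects.

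For the response rate, Section 9.4.1 plans "associated exact Clopper-Pearson 2-sided 95% and 1-sided lower 90% binomial confidence limits". It mentions no allowance for the interim stop, and it does not define the point estimate, although the raw proportion is implied. Section 9.2 defers further detail to an SAP due before data lock, which is not among the documents.

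**The concern.** Clopper-Pearson limits invert binomial tails for one sample size fixed in advance. Here the sample size depends on the data, so those tails are not the ones that generate the result, and the word exact in Section 9.4.1 no longer carries its guarantee.

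The error falls on the upper limit. That limit matters when the count is low and a reader asks whether a 30% response rate has been ruled out. The endpoint is primary in the Main Study and co-primary in the Sub-Study. A first stage that can stop for futility also pulls the average raw proportion downward.

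**Working it through.** **Inputs (Section 9.1).** Main Study: n1 = 16, stop at 0-1 responses, n = 25, reject at 5 or more. Sub-Study: n1 = 14, stop at 0-1, n = 25, reject at 5. Null 10%, alternative 30%.

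**Outcome probabilities.** Write b(x; m, p) for the binomial probability. A stopped trial has s = 0 or 1 of n1, with probability b(s; n1, p). A continued trial has s of 25 with probability Σ b(x; n1, p) · b(s − x; 25 − n1, p), summed over x ≥ 2.

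**The plan's own figures.** Summing over s ≥ 5 gives alpha 9.51% and power 90.30% (stated 9.5% and 90.3%) for the Main Study, and 9.08% and 89.06% (stated 9.1% and 89%) for the Sub-Study. Both reproduce.

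**Coverage of the planned 95% interval, Main Study.** Add the probabilities of the outcomes whose Clopper-Pearson interval misses the true rate p.

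- At p = 30%, the upper limit misses only for 0/16 (0.7^16 = 0.0033) and 2/25 (120 × 0.3² × 0.7^23 = 0.0030), total 0.0063. The lower limit misses with probability 0.0175. Coverage is 97.6%.
- At p = 31.25%, the upper limit misses for 0/16 (0.0025), 1/16 (0.0181), 2/25 (0.0021) and 3/25 (0.0132), total 0.0359. The lower limit misses from 13/25 upward, 0.0246. Coverage is 1 − 0.0605 = 93.9% (0.9395 before rounding the terms). The same interval in a fixed sample of 25 covers 95.05%.
- Over all p, coverage is below 95% only from about 0.3122 to 0.3131, with minimum 93.94%. The upper-side miss peaks at 3.6% against 2.5% nominal.

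**Sub-Study.** Coverage is below 95% only for p of about 33.9-34.9%, with minimum 94.9%. The upper-side miss reaches 3.5%. At 30%, coverage is 97.4%.

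**Upper limits computed for the design.** Order outcomes by stopping stage, then count, and find the p at which the probability of the observed outcome or a lower one is 0.025. For 2/25:

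- Main: (1−p)^16 + 16p(1−p)^15 + 120p²(1−p)^23 = 0.025 gives p = 30.8%.
- Sub: (1−p)^14 + 14p(1−p)^13 + 91p²(1−p)^23 = 0.025 gives p = 34.0%.

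| Result | Upper limit as planned | Main, for the design | Sub, for the design |
|---|---|---|---|
| 1/16 (Main, stopped) | 30.2% | 30.2% | – |
| 1/14 (Sub, stopped) | 33.9% | – | 33.9% |
| 2/25 | 26.0% | 30.8% | 34.0% |
| 3/25 | 31.2% | 33.0% | 35.1% |
| 4/25 | 36.1% | 36.6% | 37.7% |
| 5/25 | 40.7% | 40.8% | 41.3% |

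As planned, the limit at 2/25 lies below that of the stopped result, and in the Sub-Study so does the limit at 3/25 (31.2% against 33.9%). At the planned 26.0%, the lower-tail probability of 2/25 under this ordering is 6.1% (Main) or 9.3% (Sub), not 2.5%. From 7/25 upward the planned and two-stage intervals agree to within 0.1 point in both parts. In each design the two-stage interval covers at least 95.05% at every true rate.

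**Bias of the raw proportion.** Only stopped trials contribute, so bias = ((25 − n1)/25) × [b(0)(0 − p) + b(1)(1/n1 − p)].

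- Main at 30%: 0.36 × [0.0033 × (−0.30) + 0.0228 × (−0.2375)] = −0.0023, or −0.2 point. The largest is −1.1 points, near 12%.
- Sub at 30%: 0.44 × [0.0068 × (−0.30) + 0.0407 × (−0.2286)] = −0.0050, or −0.5 point. The largest is −1.6 points, near 13%.

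**UMVUE.** For s of 25 it is Σ C(n1−1, x−1)C(25−n1, s−x) / Σ C(n1, x)C(25−n1, s−x), x ≥ 2. At 2/25 in the Main Study this is 15/120 = 12.5%, against a raw 8.0%. At 4/25 (raw 16.0%) it is 17.4% (Main) or 18.6% (Sub); at 5/25 (raw 20.0%), 20.6% or 21.4%.

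**Lower 90% limit.** Its coverage is at least 90.0% at every rate in both designs. At 5/25 it is 10.06% as planned, above 10%; at 4/25 it is 7.2%. It therefore agrees with the rejection rule.

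**The case against.** The strongest reply is that nothing decisive changes, and most of it stands. The decision rule counts responses, its stated error rates are right, and the limit that matches the 1-sided test is valid. The 95% interval is conservative at almost every true rate.

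Three stronger readings are tempting, and the documents do not support them.

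- A reader might infer that coverage is 93.9% around the 30% alternative. It is 97.6% there; the shortfall occupies a window about 0.0009 wide.
- A reader might infer that a borderline-negative result would wrongly exclude 30%. At 4/25 the limit moves only from 36.1% to 36.6% (Main), and at 3/25 both versions include 30%. Only 2/25 changes sides. Its probability is 0.3% when the true Main Study rate is 30%, and it is a failed trial either way.
- A reader might infer that a reported rate from 25 patients is biased low. The downward bias is an average over both stopping points. Given continuation the raw rate is slightly high: mean 30.4% at a true 30%, and 14.1% at 10% (Main).

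The ordering is also a choice. By likelihood ratio of 30% to 10%, 2/25 gives 3² × (7/9)^23 ≈ 0.028 and 1/16 gives 3 × (7/9)^15 ≈ 0.069, so 2/25 is stronger evidence against 30%. The stage-then-count ordering instead follows the design's own futility rule and restores the coverage guarantee. That is a reason to fix the ordering in advance, not to rely on a fixed-sample method.

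The SAP foreseen in Section 9.2 could settle the point. But Section 9.4.1 names Clopper-Pearson outright, so an SAP that follows it inherits the mismatch.

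**Conclusion.** The point holds as a modest defect in reporting the primary endpoint. The planned 95% interval is not exact for this design, and its upper limits are too low by about 0.5 to 8 points at 2 to 4 responses in 25, judged by the stage-then-count ordering. The loss of coverage is at most about 1.1 points (Main) or 0.1 point (Sub), in narrow ranges of the true rate. The conclusion of either part under the rule of at least 5/25 does not change.

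The figures assume exactly 16 or 14, then 25, evaluable patients, with the stopping rule followed. Sections 4.1 and 9.0 allow at least 25 in the Main Study, so realised sizes may differ and would change the numbers. For the Sub-Study they also assume that all 14 and all 25 patients are counted at one infusion level.

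**What to change.** In Section 9.4.1 or the SAP, before data lock, state for each part that the 2-sided 95% interval is the exact two-stage interval, with outcomes ordered by stopping stage and then count, computed for the stage sizes actually realised. Report the UMVUE beside the raw proportion. Keep the 1-sided lower 90% limit, and keep Clopper-Pearson as a supplementary display if wanted.

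The cost is a sentence or two and a few lines of code. Upper limits at low response counts become somewhat higher, and readers see two point estimates. Conduct, sample size and decision rules stay as they are.

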3.1.4 Secondary Endpoints

Secondary endpoints include the following:

- PFS rate, defined as the time from registration to the time of disease progression or relapse (according to RECIST 1.1 only) or death, or the date of last tumor assessment without any such event (censored observation)
- PK profile APR-246 and concentration in plasma

- Cardiac profile of APR-246 and concentration of PLD
- The safety profile (adverse events [AEs], laboratory assessments, physical findings and biomarkers) of APR 246 and PLD chemotherapy
- Duration of response (complete or partial response)
- Progression-free survival (PFS) by assessment of CA-125
- Evaluation of potential biomarkers
- Biological activity in tumor and surrogate tissues.

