4.2 Registration of Patients

Upon completion of all screening evaluations, the center will register the patient using the Interactive Web Response System (IWRS). After successful completion of patient registration, a registration number will be issued.

Once the patient is registered through the IWRS, the patient is considered enrolled in the study. Specific instructions for the central enrollment and registration procedures are provided to the center in the study manual.

Registered patients will be assigned a unique patient identifier number. If a patient is withdrawn and replaced (as described in Section 5.3), the patient identifier number will not be reused.

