6.3 Main Study Treatment Administration

Starting within 28 days of registration, patients will receive a fixed dose of 4.5 g APR-246 (1.5 g of the dose during first 45 minutes followed by 3 g of the dose during 5 hours 15 minutes) on Days 1 to 4 with PLD 40 mg/m² on Day 4 (Figure 3). The PLD administration to be given on Day 4 only should commence 2 hours after the start of the APR-246 infusion.

Similarly for the following 28-day cycles, APR-246 will be administered on Days 1 to 4 with the PLD infusion on Day 4 starting 2 hours after the start of the APR-246 infusion.

Figure 3. Treatment Administration

Note: The entire dose should be given even if the infusion needs to be extended beyond a total time of 6 hours (e.g. due to slightly larger start volume in prefilled infusion bags).

APR-246 Treatment Duration

Treatment will be repeated every 28 days in the absence of disease progression or unacceptable toxicity. Supportive therapy, including growth factors, can be given as per institutional standard of care.

Pegylated Liposomal Doxorubicin Dosing

[figure not shown]
The dose of PLD will be calculated based on the body surface of the patients at 40 mg/m² as per standard practice at that hospital.

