7.2.3 Registration

This is performed per Section 4.2. Patients should be treated within 28 days of registration.

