8.3.3.4 Duration of Stable Disease

Stable disease is measured from the start of the treatment until the criteria for progression are met, taking as reference the smallest measurements recorded since the treatment started.

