8.3.4 Progression-free Survival

PFS is defined as the time from randomization to the time of disease progression or relapse (according to RECIST 1.1) or death, or to the date of last tumor assessment without any such event (censored observation) and includes any of the following:

- Occurrence (clinically or imaging signs) of any new lesion
- Increase in measurable and/or non-measurable tumor as defined by the RECIST 1.1 criteria

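### PFS is counted from registration (or, in 8.3.4, randomization) in a population that in practice contains only treated patients, so the wait before Cycle 1 Day 1 enters PFS as event-free time; the likely effect is small.

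*Combined protocol and SAP*

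**What the plan says.** The synopsis, 3.1.4 and 9.4.1 start PFS at registration. Section 3.1.4 has "PFS rate, defined as the time from registration to the time of disease progression or relapse", and 9.4.1 repeats that origin: "PFS is defined as the time from registration to the time of disease progression or relapse". Section 8.3.4 differs: "PFS is defined as the time from randomization to the time of disease progression or relapse". No randomization is described anywhere in the protocol.

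Registration comes after screening (4.2): "Upon completion of all screening evaluations, the center will register the patient using the Interactive Web Response System". Treatment then follows within a window (6.3): "Starting within 28 days of registration, patients will receive a fixed dose of 4.5 g APR-246". Section 6.4 gives the Sub-Study the same window, and 7.2.3 repeats it: "Patients should be treated within 28 days of registration".

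Other efficacy measures start at treatment. Best overall response does so in 8.3.2.2, and 8.3.3.4 says "Stable disease is measured from the start of the treatment until the criteria for progression are met". On-study scans are tied to cycle starts (7.2.4, Table 4 footnote 6).

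The primary efficacy population (9.3) is limited to patients with measurable disease and a p53 mutation "who have at least one radiographic assessment after pretreatment or discontinue study medication early due to disease progression". Section 5.3 replaces patients withdrawn before completing the first cycle.

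PFS is a secondary endpoint. It is summarised by Kaplan-Meier, a median, and rates at 3, 6 and 9 months.

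**The concern.** Registration is a sound origin when every registered patient is analysed. Here the clock starts at registration, but entry to the analysis depends on something that happens later. A patient who progresses or dies between registration and Day 1 has no study medication to discontinue, and no scan is scheduled in that interval. In practice that patient never enters the PFS analysis, so those who do enter carry their waiting time as event-free time. The bias always lengthens PFS. Changing 'randomization' to 'registration' in 8.3.4 would leave it in place.

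The study has no control arm, so the median and the landmark rates will be read at face value and set beside results measured from first dose. The 6-month rate deserves a separate check because the end-of-Cycle-6 scan falls shortly before that landmark.

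**Working it through.** **The plan's own figures.** The protocol gives no PFS assumption, target or sample size. Its stated operating figures concern response (9.1). For the Main Study, with X1 ~ Bin(16, p) and X2 ~ Bin(9, p), the rejection probability is the sum over x = 2 to 16 of P(X1 = x) × P(X2 ≥ 5 − x). This gives 0.0951 at p = 0.10 and 0.9030 at p = 0.30, against 9.5% and 90.3% stated. The Sub-Study rule (14, then 25 in total) gives 0.0908 and 0.8906, against 9.1% and 89%. All reproduce, and none involves the PFS origin.

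**How long the gap can be.** Pretreatment evaluations, including the baseline scan, must fall within 28 days before Day 1 (7.2.2, 8.2, Table 4 footnote 1), and registration follows their completion (4.2). If the baseline scan precedes registration by d days, the gap g is at most 28 − d. A gap of 28 days needs all screening done on the day of registration. A gap of 15 days needs the scan no more than 13 days before registration. The protocol gives no expected gap.

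**Median.** For each patient, PFS from registration = g + PFS from Day 1. With a common gap, the median is longer by exactly g. The ceiling of 28 days is 28 / 30.44 = 0.92 month.

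**6-month rate, smooth model.** Assume exponential PFS from Day 1 with median m, so S(t) = 2^(−t/m). The registration clock reads S(t − g).

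- m = 3 months: 25.0% with no gap, 26.4% at 7 days (+1.4), 27.8% at 14 days (+2.8).
- m = 4 months: 35.4%, 36.8% (+1.4), 38.3% (+2.9).
- m = 5.5 months: 46.9%, 48.3% (+1.4), 49.7% (+2.8).
- At the 28-day ceiling the rise is 5.8 to 6.1 points across these medians.

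**6-month rate, scan schedule.** Suppose progression is found only at on-time scans. These fall about 52–56, 108–112, 164–168 and 220–224 days after Day 1. Six months is 182.6 days.

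- The end-of-Cycle-6 scan stays before the landmark while g is at most 182.6 − 168 = 14.6 days (scan at the end of its window) or 182.6 − 164 = 18.6 days (scan at the start). Up to that point the rate does not move.
- Beyond it, the rate reflects the end-of-Cycle-4 scan. With mid-window scans (days 166 and 110), it steps from 28.4% to 43.4% (m = 3), 38.9% to 53.5% (m = 4) and 50.3% to 63.4% (m = 5.5). That is 15.0, 14.6 and 13.1 points if every patient has such a gap.
- With mixed gaps the step scales with the share of patients beyond the threshold. If one in five were beyond it, the shift would be 0.2 × 13.1 to 0.2 × 15.0, about 2.6 to 3.0 points.

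**3 and 9 months.** On the same schedule neither rate moves for any gap from 0 to 28 days. The first scan plus 28 days falls by day 84, before day 91.3, and the second is no earlier than day 108. The end-of-Cycle-8 scan plus 28 days falls by day 252, before day 273.9, and the next is no earlier than day 276. In the smooth model a 14-day gap adds 4.1 to 5.6 points at 3 months and 1.4 to 1.9 at 9 months. Deaths, and progression found between scans, would behave partly in this way.

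**The case against.** Registration is prespecified in three places, is the point of enrolment (4.2), and is a legitimate origin in a single-arm trial. Response and stable-disease duration are different measures and need not share it. A reader might infer from their different origins that the PFS origin is an error in itself. The documents do not support that; the case rests on the mismatch between the origin and the population in 9.3.

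A reader might also take the 28-day window as the typical distortion, or the 13 to 15 points as the expected inflation of 6-month PFS. Neither follows, because screening and the gap share the same 28 days.

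The exponential model also holds disease still during the wait. In fact the baseline scan precedes registration and progression is judged against it, so growth while waiting could bring progression earlier on a Day 1 clock. This weakens any comparison of short-gap and long-gap patients as if their disease courses were the same. It does not affect the identity that registration-based PFS equals the gap plus Day 1 PFS.

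Finally, a Day 1 origin is not a complete cure. Cycles can be delayed (6.5.2.1), and a cumulative delay of about 15 to 19 days would still push the end-of-Cycle-6 scan past 6 months. A treated patient who dies of another cause before the first scan still falls outside 9.3. Both limits stand.

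**Conclusion.** The point holds at modest size. The clock starts before the event that in practice admits a patient to the analysis, so PFS is lengthened by the wait, always in the favourable direction. The likely lengthening of the median is days to about two weeks. That is a judgement from the screening window, since no expected gap is given. For gaps of 7 to 14 days the 6-month rate rises by about 1 to 3 points in the smooth model and by nothing on the scan schedule. The 13 to 15 point step is an extreme bound: it needs all patients to have gaps above about 15 to 19 days, with on-time cycles and progression found only at scheduled scans. All rates assume exponential medians of 3 to 5.5 months, which the protocol does not state.

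A reader might infer that the trial's conclusion is at risk. It is not: PFS is descriptive, with no threshold or test, and response rate, alpha, power and stopping rules do not depend on it. The change is still worth making because it is cheap, removes a one-directional bias, and 8.3.4 has to be edited in any case.

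**What to change.** In the synopsis, 3.1.4, 8.3.4 and 9.4.1, define PFS for the efficacy-evaluable population from Cycle 1 Day 1 (first dose), replacing both 'registration' and 'randomization'. Evaluate the median and the 3-, 6- and 9-month rates on that clock. Report registration-based PFS as a sensitivity analysis, with the distribution of the registration-to-Day-1 interval.

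If the sponsor keeps registration as the primary origin, use it in all four places and add Day 1 PFS as the sensitivity analysis, again with the interval reported.

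The cost is wording in four places and one table, which the SAP promised in 9.2 before data lock can carry. Reported PFS becomes slightly shorter. Neither option removes the effect of cycle delays on scan timing or the exclusion of treated patients who die of other causes before a first scan; the report should say so.

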Objectives, Endpoints and Study Treatment: Main Study Objectives: Primary Objectives: 
To assess the preliminary efficacy of APR-246 with PLD chemotherapy in patients with platinum-resistant HGSOC with mutated TP53 Secondary Objectives: 
To evaluate the pharmacokinetics (PK) of APR-246 when administered with PLD chemotherapyTo evaluate cardiac safety of APR-246 when administered with PLD chemotherapyTo assess the safety and tolerability of APR-246 with PLD chemotherapy in patients with platinum-resistant HGSOC with mutated TP53	

- To assess:
 - Duration of response (complete or partial response)
 - Progression-free survival (PFS) by assessment of cancer antigen 125 (CA-125)
 - PFS by RECIST 1.1
- To evaluate potential biomarkers and tumor activity based on CA-125
To assess the biological activity in tumor and surrogate tissues

Main Study Endpoints:

Primary Endpoints:

- Overall response rate according to RECIST 1.1

Secondary Endpoints:

- PFS rate, defined as the time from registration to the time of disease progression or relapse (according to RECIST 1.1 only) or death, or the date of last tumor assessment without any such event (censored observation)
- PK profile of APR-246 and concentration in plasma
- Cardiac profile of APR-246 and concentration of PLD
- The safety profile (adverse events [AEs], laboratory assessments, physical findings and biomarkers) of APR-246 and PLD chemotherapy
- Duration of response (complete or partial response)
- Progression-free survival (PFS) by assessment of CA-125
- Evaluation of potential biomarkers
- Biological activity in tumor and surrogate tissues

Objectives, Endpoints and Study Treatment:

Sub-study Objectives: Same as Main Study Objectives, except safety and tolerability, in addition to preliminary efficacy, are Primary Objectives.

Sub-Study Primary Endpoints: The safety profile (adverse events [AEs], laboratory assessments, physical findings and biomarkers) of APR-246 with a shorter infusion and PLD chemotherapy; overall response rate according to RECIST 1.1.

Diagnosis and Main Criteria for Inclusion:

Inclusion Criteria:

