6.6 Concomitant Treatment and Prohibited Medication

Patients are allowed to receive supportive care therapies (including cytokine growth factors) concomitantly during the trial.

No anti-cancer therapy other than that given in this clinical trial; no immunotherapy; no hormonal cancer therapy; no radiation therapy (except palliative); and no experimental medications are permitted during the trial. No PARP inhibitors are permitted after a beneficial response to study therapy.

Radiation therapy to index lesions should be avoided where possible; when deemed essential for patient well-being, the sponsor must be informed as the patient will become non-evaluable for endpoints assessed by RECIST, i.e. response rate and PFS.

Concomitant use of paracetamol-based compounds is allowed. However, caution should be taken when co-administering APR-246 with high doses of paracetamol (i.e., 4 g/24 h). Use of paracetamol must be terminated if any liver function tests increase above normal ranges.

Any disease progression that requires other specific antitumor therapy will be cause for discontinuation from the trial.

Anticoagulant Therapy: Patients who are taking warfarin may participate in this trial; however, it is recommended that prothrombin time (international normalized ratio [INR]) is monitored carefully at least once per week for the first month, then monthly if the INR is stable. Subcutaneous heparin is permitted.

Concurrent or procedural medications or therapy given to or taken by the patient will be recorded in the CRF along with the indication. All concomitant medication should be recorded for up to 30 days following the last protocol treatment. After this period, only relevant medication (e.g., medication in patients with treatment-related AEs) will be recorded in the CRF.

Both generic and trade names may be recorded. However, the generic name is generally preferred because of its specificity, whereas trade names are preferred for combination products.

The potential interaction of APR-246 with other medicinal products has not been investigated.

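### Duration of response does not end at death, the radiation rule in 6.6 conflicts with the efficacy population in 9.3, and PFS is worded unevenly across sections

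*Combined protocol and SAP*

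**What the plan says.** **DOR.** It is a listed secondary endpoint (3.1.4). Section 8.3.3.2 runs it from first recorded CR or PR to objectively documented recurrence or progression. It names neither death nor a censoring date. Section 9.4.1 has no DOR analysis.

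**Radiation to index lesions.** Section 6.6 states that "the patient will become non-evaluable for endpoints assessed by RECIST, i.e. response rate and PFS". Section 9.3 admits to the efficacy population any patient with measurable disease and a p53 mutation who has "at least one radiographic assessment after pretreatment or discontinue study medication early due to disease progression". It does not mention radiation, and neither does 9.4.1.

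**PFS.**
- Synopsis and 3.1.4: "PFS rate, defined as the time from registration to the time of disease progression or relapse (according to RECIST 1.1 only) or death", censored at the last tumor assessment.
- Section 8.3.4: "PFS is defined as the time from randomization to the time of disease progression or relapse (according to RECIST 1.1) or death", also censored at the last tumor assessment, with a list that includes "Occurrence (clinically or imaging signs) of any new lesion".
- Section 9.4.1: "PFS is defined as the time from registration to the time of disease progression or relapse (according to RECIST 1.1 only) or death", followed by "Patients who do not experience a PFS event will be censored at their last clinic visit contact for the assessment of disease progression".

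Section 9.2 promises an SAP before data lock. None is in the supplied text.

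**The concern.** A responder who dies without documented progression has a PFS event but, read literally, no DOR event. Not counting such deaths can lengthen DOR.

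In 6.6 and 9.3 the same patient is out under one section and in under the other. Removing patients because of something that happens after baseline can bias the result. A patient who needs radiation to an index lesion may be doing worse than average, so removal can flatter PFS and the response rate; a responder irradiated later would take a response out with her. Because 6.6 names response rate, the primary endpoint is involved.

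The PFS differences are lesser. They leave the handling of a few patients open in an open-label trial whose detailed analysis rules are still to be written.

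**Working it through.** **1. The plan's own figure.** PFS and DOR have no stated sample size or power. For the response test, P(reject) = sum over x from 2 to 16 of P(X1 = x) × P(X2 ≥ 5 − x), with X1 ~ Bin(16, p) and X2 ~ Bin(9, p). At p = 10% this gives 0.0951 and at p = 30% 0.9030, matching the stated 9.5% and 90.3%. The Sub-Study design (14 then 11) gives 0.0908 and 0.8906, matching 9.1% and 89%. Nothing below alters these calculations.

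**2. DOR.** Assume a Kaplan-Meier median (first time S ≤ 0.5), all other responders progressing, and one death censored near its date with the order unchanged. With 5 responders and every end counted, S falls 0.8, 0.6, 0.4, so the median is the third duration. If the second-ordered end is an uncounted death, S is 0.8, then 0.8 × 2/3 = 0.53, then 0.53 × 1/2 = 0.27, so the median moves to the fourth. Over all positions of the death, the median moves to the next ordered duration in 2 of 5, 3 of 6, 3 of 7 and 4 of 8 positions for 5, 6, 7 and 8 responders. Otherwise it does not move.

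**3. Radiation and PFS.** Compare one such patient among 25 censored at her last scan before radiation (week w) with the same patient removed. If S is the 6-month rate in the others and Sw = S^(w/26), the difference is (S/Sw)(1 − Sw)/25. Example: S = 45%, w = 16 gives Sw = 0.612, and 0.735 × 0.388/25 = 1.1 points. Across S of 35-55% the results are:

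| Last scan before radiation | Difference (points) |
|---|---|
| Week 8 | 0.4-0.5 |
| Week 16 | 1.0-1.3 |
| Week 24 | 1.6-2.3 |

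**4. Radiation and response rate.** With 5 responses in 25 the rate is 20.0%. Removing one irradiated non-responder gives 5/24 = 20.8%; removing one irradiated responder gives 4/24 = 16.7%. The rule in 9.1 is written for 25 evaluable patients and does not say what applies at 24.

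**5. New-lesion bullet in 8.3.4.** Simulation with 400,000 patients per setting. Assumed: exponential first event with median 14-26 weeks, 0-20% of first events deaths, scans about every 8 weeks (SD 0.7 week), and 4% or 8% of progressing patients with a clinically seen new lesion. If they are never scanned again and no death is recorded, censoring them at the last scan puts 6-month PFS 0.9-1.2 points (4%) or 1.8-2.5 points (8%) above counting an event at the clinical date. At median 20 weeks, 10% deaths and a 4% share the rates are 44.4% and 43.2%. If a scan confirms the lesion about 4 weeks later, the gap is about 0.1 or 0.2 points.

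**6. Censoring date.** With scans exactly every 8 weeks and no deaths between scans, events fall only on scan dates, so moving a censoring date between two scans changes no risk set and the gap is zero. With scan-date scatter, some deaths and 10-30% dropout over 52 weeks, last scan versus last 4-weekly visit differs by 0.2-0.6 points. With scans 0-4 days before a cycle a run gave up to 0.9.

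**7. No post-baseline scan.** One early progressor among 25, counted as an early event versus censored at registration: S/25 = 1.4, 1.8 or 2.2 points at S = 35, 45 or 55%. Counted early versus at a death after month 6: 1/25 = 4.0 points.

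**8. Scale.** The 95% half-width of a 6-month rate is 1.96 × sqrt(S(1 − S)/25) = 18.7 to 19.5 points for S of 35-55%.

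**The case against.** Much of the PFS material is weaker than it first looks.

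- **Start date.** The word randomization in 8.3.4 is a leftover. Nobody is randomized, every other section says registration, and only one date is usable. This stands: the change is editorial.
- **Clinical progression.** A reader might infer that 8.3.4 adds clinical progression as an event that 9.4.1 excludes. The documents do not support that. Section 8.3.4 cites RECIST 1.1 and its bullet concerns new lesions, not general worsening. PFS by CA-125 is a separate endpoint, so restricting 3.1.4 and 9.4.1 to RECIST plausibly just excludes CA-125 progression. Section 8.2 accepts superficial clinical lesions, and 8.3.2.1 speaks of repeat scans only for an equivocal new lesion.
- **Censoring.** A reader might infer that 9.4.1 censors at any clinic visit. Its wording ties the contact to assessing progression, which most naturally means a tumor assessment.
- **Patients without a scan.** Section 5.3 makes RECIST progression the stopping reason, 7.2.5 requires an end-of-treatment scan, and 7.2.4 continues 8-weekly scans after stopping without progression. The group should be small.
- **Radiation.** Section 6.6 could mean not evaluable from that point on, which for PFS amounts to censoring. That reading is possible, but neither 9.3 nor 9.4.1 adopts it.
- **DOR.** Death is omitted rather than expressly excluded, and the median in the working assumes a method that 9.4.1 never specifies. The size is therefore illustrative; the omission is in the text.

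**Conclusion.** Two defects change an analysis if the text is followed literally: DOR does not end at death, and 6.6 and 9.3 disagree about the irradiated patient. The remaining PFS differences call for harmonization.

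Effects are small and descriptive: mostly under about 2 points of 6-month PFS per affected patient, against a half-width of about 19. The exception is a patient without a scan whose only recorded event is a death after month 6 (4.0 points). Every share, median and dropout rate used is an assumption; the documents give none of them.

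A reader might infer that the primary test is miscalibrated. It is not: its stated alpha and power reproduce and do not change. The opposite inference, that the primary endpoint is untouched, also fails, because 6.6 names response rate and so bears on who is in the denominator. The rules should be settled before data lock.

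**What to change.** 1. **8.3.3.2 and 9.4.1:** define DOR from first documented response to RECIST 1.1 progression or death from any cause, censored at the last adequate tumor assessment, and state the analysis.
2. **6.6 and 9.3:** reconcile them so that a patient with radiation to index lesions stays in the efficacy population and the response-rate denominator, with PFS censored at the last adequate assessment before radiation.
3. **8.3.4:** replace randomization with registration and refer the new-lesion bullet to 8.3.2.1. This keeps the superficial clinical lesions that 8.2 accepts.
4. **9.4.1:** censor at the last adequate tumor assessment, or at registration if there is none and no death. Align the synopsis and 3.1.4.
5. Report the number of patients without a post-baseline assessment. A sensitivity analysis counting discontinuation for clinical progression as an event is optional; the stopping reasons in 5.3 do not clearly record it.

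The cost is wording in these sections, or in the SAP promised in 9.2 together with corrected protocol text, and one count. Items 1 to 4 need no new visits or scans. DOR may come out shorter. Censoring at radiation still assumes that it is not informative, but it keeps the follow-up before radiation that removal would discard.
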